5. ENDPOINTS AND COVARIATES

Visual analog scale (VAS) data will be similarly rescaled prior to any calculation and analysis as in the main LTE study. Refer to main LTE study [Section 6](#) for the details. *The baseline will be the latest value obtained prior to the first dose of the sub-study.*

5.1. Primary Endpoints

- Δ HAQ-DI at 6 months.
- Δ PASDAS at 6 months.

5.2. Secondary Endpoints

- Δ HAQ-DI score at all time points except Month 6 (see [Appendix 2.2](#)).
- Δ PASDAS at all time points except Month 6 (see [Appendix 2.9](#)).
- PsARC response at all time points (see [Appendix 2.4](#)).
- Δ PGA-PsO at all time points (see [Appendix 2.11](#)).
- % Δ BSA at all time points (see [Appendix 2.10](#)).
- Δ DSS at all time points.
- Dactylitis absence at all time points.
- Δ in Enthesitis score (using LEI) at all time points.
- Enthesitis absence (using LEI) at all time points.
- MDA response at all time points (see [Appendix 2.8](#)).
- Δ in ACR components (tender/painful joint count (68), swollen joint count (66), Physician's Global Assessment of Arthritis, Patient's Global Assessment of Arthritis, Patient's Assessment of Arthritis Pain, CRP) at all time points (see [Appendix 2.1](#)).

- *Physical function/other patient reported outcomes to be assessed at all time points: Δ Short-Form 36 (version 2, Acute) (see [Appendix 2.17](#)); Δ FACIT-F (see [Appendix 2.16](#)); Δ EQ-5D-3L (see [Appendix 2.15](#)); EQ-VAS.*
- *Incidence and severity of adverse events.*
- *Incidence of clinical abnormalities and change from baseline (see [Appendix 6](#) Section 5 for baseline definition) in clinical laboratory values during treatment.*

5.3. Other Endpoints

- *Δ DAS28-3 (CRP) at all time points (see [Appendix 2.3](#)).*
- *MDA component response (yes/no) at all time points.*
- *Δ PGJS-VAS at all time points.*
- *Incidence of investigator-reported clinically significant changes in physical examination from baseline during treatment.*
- *Incidence of electrocardiogram (ECG) abnormalities and change from baseline in ECG measurements during treatment.*
- *Incidence of vital sign (blood pressure and pulse rate) abnormalities and changes from baseline in vital sign measurements during treatment.*

5.4. Covariates

Mixed Model for Repeated Measures (MMRM) will be used for analyzing continuous efficacy endpoints collected over multiple visits (eg, Δ HAQ-DI or Δ PASDAS). The baseline value will be included in the model as a covariate.

6. HANDLING OF MISSING VALUES

For the SF-36v2, EQ-5D-3L and FACIT-F instruments, the same approaches as for the main LTE study will be followed. Refer to main LTE study [Section 7](#) for the details. In general, missing values will not be imputed. For the binary efficacy endpoints (eg, PsARC Response), missing responses will be treated as non-response (MR=NR).

7. STATISTICAL METHODOLOGY AND STATISTICAL ANALYSES

Both the efficacy and safety analysis will base on data collected in the sub-study only unless noted otherwise.

There are two treatment groups in the sub-study: Tofacitinib 5 mg BID + MTX placebo and Tofacitinib 5 mg BID + MTX. Subjects will be analyzed and reported by treatment groups.

Efficacy will also be assessed for a subset of the subjects who had more severe PsA as defined by ≥ 5 swollen or tender joints at the baseline of the sub-study, if sample size permits.

7.1. Statistical Methods

7.1.1. Analyses for Continuous Data

For the continuous endpoints, by-visit summary statistics (N, mean, standard deviation, standard error of the mean, minimum, 1st, 2nd (median) and 3rd quartiles and maximum) will be provided by treatment group for both the original and the change (or for some measures, percent change, eg, %ΔBSA) from baseline values over 12 months.

In addition, *continuous efficacy endpoints collected over multiple visits (eg, ΔHAQ-DI or ΔPASDAS) will be analyzed using a Mixed Model for Repeated Measures (MMRM) without imputation for missing values on the FAS.* The MMRM model will include fixed effects of treatment (Tofacitinib + Placebo and Tofacitinib + MTX), visit, treatment by visit interaction, and baseline value. The model will fit a common unstructured variance-covariance matrix for both treatment groups. If the unstructured matrix fails to converge, heterogeneous compound symmetry (CSH) will be attempted. *Treatment comparison between the 2 groups at each post-baseline time point will be generated from this model providing both 2-sided p-value and 95% CI.*

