9.1. Sample Size Determination

This is an estimation study. The primary objective will be met by estimating the effect of each treatment and their difference. A sample size of 90 subjects per group was selected such that the 2-sided 95% confidence interval (CI) half-width for the difference in Δ HAQ-DI at Month 6 between tofacitinib 5 mg BID + placebo and tofacitinib 5 mg BID + MTX would be approximately 0.18 assuming a common standard deviation (SD) of 0.6 for both groups. Similarly this sample would yield a 2-sided 95% CI half-width of approximately 0.47 for the difference in Δ PASDAS at Month 6 between the 2 treatment groups assuming a common SD of 1.6 for both groups.

No adjustment for multiple comparisons will be made in the analyses. Nominal statistical significance will be claimed if the 2-sided p value is ≤ 0.05 .

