7.2.1. Analysis of Primary Endpoints

For each of the two primary endpoints in the sub-study: Δ HAQ-DI at Month 6 and Δ PASDAS at Month 6, a MMRM described in Appendix 6 [Section 7.1.1](#) on the FAS without imputation for missing values will be used to estimate the change from baseline at Month 6 for each treatment group. The treatment comparison between the 2 groups at Month 6 will also be generated from this model providing both 2-sided p-value and 95% CI. The analysis will include all the data through Month 12. Treatment comparisons between the 2 treatment groups at other visits will be made as well from this model.

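### The sub-study MMRM is valid but not fully efficient: it fits one baseline slope for all visits and leaves out earlier pre-randomisation LTE values of the same endpoint.

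*SAP*

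**What the plan says.** SAP Appendix 6, Section 7.1.1, fits continuous efficacy endpoints with an MMRM containing treatment, "visit, treatment by visit interaction, and baseline value", and an unstructured covariance common to both arms. Section 5.4 names one covariate: "The baseline value will be included in the model as a covariate". Section 5 defines baseline as the last value before the first sub-study dose. For the primary endpoints, Section 7.2.1 adds "The analysis will include all the data through Month 12", so five post-baseline visits (Months 1, 3, 6, 9 and 12) share the one slope. No baseline-by-visit term and no earlier LTE value appears.

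Protocol Appendix 10, Section 9.1, describes an estimation study sized on the "2-sided 95% confidence interval (CI) half-width". "A sample size of 90 subjects per group was selected" to make it "approximately 0.18 assuming a common standard deviation (SD) of 0.6 for both groups" for HAQ-DI. For PASDAS the target is a "2-sided 95% CI half-width of approximately 0.47", "assuming a common SD of 1.6 for both groups".

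Every entrant has at least 24 months in the LTE (Protocol Appendix 10, Section 4.1). HAQ-DI is taken at every LTE visit. SF-36, a PASDAS component, is taken at Month 1, Month 6 and six-monthly after that (Protocol Section 2.2.2), and PASDAS is missing if any component is missing (SAP Appendix 2.9). Protocol Appendix 10, Section 9.2, and SAP Appendix 6, Section 7, limit the sub-study efficacy analysis to sub-study data; the SAP allows for exceptions that are noted.

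**The concern.** There are two possible losses of precision.

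- **One slope for all visits.** If the correlation with the switch-visit value falls over time, the right adjustment differs by visit. The common slope is pulled towards the early visits, where residual variance is smallest, and fits Months 6 and 12 less well.
- **One baseline value.** A single reading on a single day is a noisy measure of a subject's level. Earlier readings of the same endpoint already exist and precede randomisation.

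The sub-study has no formal hypothesis and no decision rule (SAP Appendix 6, Section 3). Its main product is the interval for the Month 6 difference, so precision available without new data serves its stated purpose.

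**Working it through.** **Step 1. Reproduce the plan's figures.** Half-width = 1.96 × SD × √(2/90).

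- HAQ-DI: 1.96 × 0.6 × 0.1491 = 0.175 (0.177 with t on 178 df). Stated: 0.18.
- PASDAS: 1.96 × 1.6 × 0.1491 = 0.467 (0.471 with t). Stated: 0.47.

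Both reproduce. The formula is the unadjusted two-sample one, with no covariate and no dropout.

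**Step 2. Inputs.** From the protocol: SD of change 0.6, 90 per arm, visits at Months 1, 3, 6, 9 and 12. Assumed, because the documents do not give them: HAQ-DI SD 0.65 at every visit, an earlier LTE value 3 months before the switch, complete data, and three correlation shapes (constant; exponential decay; slower decay, exponential in the square root of time) with 0, 10 or 20% visit-level noise. Each is calibrated so that the six-month correlation is 1 − 0.6²/(2 × 0.65²) = 0.574. Noise makes no difference to the constant shape after calibration, which leaves seven distinct patterns.

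**Step 3. Formulas.** Let R be the residual covariance given the switch value and b_k the true slope of the visit-k value on it. (Modelling change subtracts 1 from every slope and alters nothing below.)

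- Common slope reached by the planned fit: b* = (1′R⁻¹b)/(1′R⁻¹1).
- Variance of the visit-k difference, planned: (2/n)[R_kk + (b_k − b*)² × 0.65²].
- (a) With baseline-by-visit: (2/n)R_kk.
- (b) With the earlier value as well: R_kk becomes the residual variance given both pre-randomisation values.

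**Step 4. Two worked cases at Month 6.** In every pattern R_66 = 0.4225 × (1 − 0.574²) = 0.2833.

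- *Exponential decay, no noise.* b_6 = 0.574 and b* = 0.840. Planned: 0.2833 + 0.266² × 0.4225 = 0.3132. Ratio 0.2833/0.3132 = 0.905, and half-width 0.1635 → 0.1555. The earlier value adds nothing here.
- *Constant correlation.* The slope term gains nothing. With the earlier value: 0.4225 × (1 − 2 × 0.574²/1.574) = 0.2456. Ratio 0.2456/0.2833 = 0.867, and half-width 0.1555 → 0.1448.

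**Step 5. All patterns, HAQ-DI, SD of change 0.6.**

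| Pattern | Half-width M6: planned / (a) / (a)+(b) | M6 variance cut: (a) / (a)+(b) | M12 variance cut: (a) |
|---|---|---|---|
| Constant | 0.1555 / 0.1555 / 0.1448 | 0 / 13.3% | 0 |
| Exponential, 0% noise | 0.1635 / 0.1555 / 0.1555 | 9.5% / 9.5% | 22.6% |
| Exponential, 10% | 0.1582 / 0.1555 / 0.1550 | 3.4% / 4.0% | 13.1% |
| Exponential, 20% | 0.1562 / 0.1555 / 0.1535 | 0.9% / 3.5% | 6.5% |
| Slower, 0% | 0.1570 / 0.1555 / 0.1525 | 1.9% / 5.7% | 6.3% |
| Slower, 10% | 0.1561 / 0.1555 / 0.1513 | 0.8% / 6.1% | 3.6% |
| Slower, 20% | 0.1557 / 0.1555 / 0.1499 | 0.3% / 7.4% | 1.7% |

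Equivalent extra subjects for both changes: 180 × (1/0.965 − 1) ≈ 7 to 180 × (1/0.867 − 1) ≈ 28. No pattern shows a loss.

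**Step 6. PASDAS.** Entrants at Months 24, 30 or 36 have their previous scheduled PASDAS 6 months back; entrants at Months 27 or 33 have it 3 months back. With a 6-month lag and the same assumed correlations, the smallest joint gain is about 2.4% in variance (exponential decay, 20% noise).

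**The case against.** The strongest reply is that nothing is wrong. Baseline adjustment in an MMRM with unstructured covariance is an adequate choice. At the protocol SD with complete data it gives 0.156 to 0.164, already inside the planned 0.18. The gain of 0.003 to 0.011 HAQ-DI units is small beside the 0.30 and 0.35 responder thresholds that the SAP uses for the main study (Section 5.4.1). All of that stands, and it is why this is an improvement and not a correction. The 0.18 and 0.47 do, however, allow for no dropout, and Protocol Appendix 10, Section 3, permits discontinuation for deteriorating response, so spare precision has a use.

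The earlier-value covariate also conflicts with the sub-study-data-only rule, and filling in a missing earlier value sits awkwardly beside the plan's statement that missing values are not imputed. Both need explicit wording. Earlier values may also predate the step-down from 10 mg BID, the switch to oral MTX or the end of injected steroids (Protocol Appendix 10, Section 4.1). That would weaken their correlation with Month 6 and make the gains above optimistic. It would not bias a randomised comparison.

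The interaction alone does little in most patterns. It exceeds a 3.5% Month 6 gain only under steady decay without noise.

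**Conclusion.** The point holds as a modest loss of efficiency. At SD of change 0.6, the interaction alone lowers the Month 6 HAQ-DI variance by 0 to 9.5% and the Month 12 variance by 0 to 23%. Both changes together lower the Month 6 variance by about 3.5 to 13%. For PASDAS the minimum is about 2.4%. The direction is the same in every pattern tried; the size rests on assumed correlations, large-sample formulas and complete data.

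Three stronger readings are not supported.

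- A reader might infer that the comparison is biased. It is not: misfitting a baseline slope costs precision under randomisation, not validity.
- A reader might infer that the sample-size statement is wrong. Both half-widths reproduce.
- A reader might infer a gain as large as 18.7%, or 41 subjects. That needs an SD of change of 0.45 with constant correlation. The protocol gives 0.6, and at 0.45 the planned half-width would already be about 0.123.

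**What to change.** **(a) Recommended, essentially free.** In SAP Appendix 6, Sections 5.4 and 7.1.1, add the baseline-by-visit interaction. This costs four more parameters on about 180 subjects and one line of code, and uses sub-study data only.

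**(b) Optional, cheap.** Add the last pre-switch LTE value of the same endpoint, with its visit interaction (five more parameters): HAQ-DI from the previous LTE visit, PASDAS from the last previous visit at which it could be scored. Write an exception for this pre-randomisation covariate into SAP Appendix 6, Section 7, and Protocol Appendix 10, Section 9.2. State that a missing earlier value is replaced by the overall mean, and that this is covariate handling and not outcome imputation. The cost is an amendment to both documents, made before unblinding.

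No new data are needed, and (a) can be adopted without (b).

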7.1.2. Analyses for Categorical Data

The data for all categorical endpoints (including binary) will be summarized by contingency tables that show the counts/frequency of the response at each visit by treatment group. For some categorical endpoints, such as the presence or severity of adverse events, contingency or frequency tables will consider the data over the entire duration of the study and will not be constructed at each time point.

Two-sided p-value and 95% CI will be generated by normal approximation to the binomial distribution approach for the treatment comparison between the 2 groups. Let N be number of subjects assessed at each visit, n be number of responders, and $\hat{p} = n/N$ be the observed responder rate. Use subscript t to refer to the treatment group (Tofacitinib + Placebo) and c to refer to the treatment group (Tofacitinib + MTX). Then the normal approximation to the 2-sided p-value will be calculated as

$$2Pr\left\{Z \geq \left| \frac{\hat{p}_t - \hat{p}_c}{\sqrt{\frac{\hat{p}_t(1-\hat{p}_t)}{N_t} + \frac{\hat{p}_c(1-\hat{p}_c)}{N_c}}} \right| \right\},$$

where Z is Normal (0, 1) distributed.

Two-sided 95% CI will be formed by

$$(\hat{p}_t - \hat{p}_c) \pm 1.96 \sqrt{\frac{\hat{p}_t(1-\hat{p}_t)}{N_t} + \frac{\hat{p}_c(1-\hat{p}_c)}{N_c}}.$$

If there is no (ie, 0) response or 100% response in any of treatments, 0.5 will be added to the number of responses and 1 will be added to the denominator in each treatment corresponding to the pair of comparison for calculating the treatment difference, standard error, 95% CI and 2-sided p-value (Agresti, 2002).

When response rate of 0% or 100% is observed in both treatments in comparison, no formal comparison will be performed. Estimated response rate of 0% or 100% will be reported as observed.

The final results will be expressed in percentages, ie, (proportions x 100)%.

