9.3. Efficacy Analysis

The Full Analysis Set (FAS) will include all subjects who were randomized to the sub-study and received at least one dose of the sub-study drug (tofacitinib, MTX or placebo). The primary efficacy population for this study is defined by the FAS.

Continuous endpoints for which change or percent change from baseline is the measure to be analyzed, would require that a subject have a baseline value and at least one post-baseline value to be included in the FAS for that endpoint.

For all the efficacy and PRO endpoint analyses, the baseline will be the latest value obtained prior to the first dose of the sub-study.

Continuous endpoints collected over multiple visits (eg, Δ HAQ-DI or Δ PASDAS) will be analyzed using a Mixed Model for Repeated Measures (MMRM) without imputation for missing values on the FAS. Treatment comparison between the 2 groups at each post-baseline time point will be generated from this model providing both 2-sided p-value and 95% CI.

Binary endpoints (eg, MDA response) will be analyzed using the normal approximation for the difference in binomial proportions with missing response as non-response (MR=NR) on the FAS. Treatment comparison between the 2 groups at each post-baseline time point will be generated providing both 2-sided p-value and 95% CI.

Efficacy will also be assessed for a subset of the subjects who had more severe PsA as defined by ≥ 5 swollen or tender joints at the baseline of the sub-study, if sample size permits.

Complete details will be specified in the SAP.

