Appendix 6. Methotrexate Withdrawal Sub-Study

1. INTRODUCTION

The purpose of this sub-study is to assess the efficacy, safety and tolerability of tofacitinib 5 mg BID administered as monotherapy after methotrexate (MTX) withdrawal compared to tofacitinib 5 mg BID continued in combination with MTX in subjects with active PsA. Subjects who have completed at least 24 months of participation in the long term extension study A3921092 and are currently receiving methotrexate may be included.

Subjects will be randomized to the 2 treatment arms in a 1:1 ratio, one in which they will receive open label tofacitinib 5 mg tablets BID and blinded methotrexate capsules (oral dose range from 7.5 mg to 20 mg per week) and the second in which they will receive open label tofacitinib 5 mg tablets BID and blinded MTX placebo capsules. The sub-study will be approximately 12 (standardized 4-week) months in duration and visits will occur at Baseline, Months 1, 3, 6, 9 and 12. The sub-study baseline will occur at the same time as a scheduled study visit at or after Month 24 of A3921092. This visit will be referred to as Sub-study Switch Visit or Baseline visit (Sub-study Switch/Baseline visit).

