7.2.2. Analysis of Secondary and Other Efficacy/Health Outcome Endpoints

The MMRM described in Appendix 6 [Section 7.1.1](#) will be used on FAS or endpoint specific FAS for:

- *Δ HAQ-DI score at all time points except Month 6* (see [Appendix 2.2](#)). Note that this will be accomplished by the same MMRM analysis in Appendix 6 [Section 7.2.1](#).
- *Δ PASDAS at all time points except Month 6*. Note that this will be accomplished by the same MMRM analysis in Appendix 6 [Section 7.2.1](#).
- *Δ PGA-PsO at all time points* (see [Appendix 2.11](#)).
- *% Δ BSA at all time points* (see [Appendix 2.10](#)).
- *Δ DSS at all time points*.
- *Δ in Enthesitis score (using LEI) at all time points*.
- *Δ in ACR components (tender/painful joint count (68), swollen joint count (66), Physician's Global Assessment of Arthritis, Patient's Global Assessment of Arthritis, Patient's Assessment of Arthritis Pain, CRP) at all time points* (see [Appendix 2.1](#)).
- *Physical function/other patient reported outcomes to be assessed at all time points: Δ Short-Form 36 (version 2, Acute) (see [Appendix 2.17](#)); Δ FACIT-F (see [Appendix 2.16](#)); Δ EQ5D (see [Appendix 2.15](#)); EQ-VAS.*

- Δ DAS28-3 (CRP) at all time points (see [Appendix 2.3](#)).
- Δ PGJS-VAS at all time points.

The analysis methods described in Appendix 6 [Section 7.1.2](#) will be used on the FAS or endpoint specific FAS for:

- PsARC response at all time points (see [Appendix 2.4](#)).
- Dactylitis absence at all time points.
- Enthesitis absence (using LEI) at all time points.
- MDA response at all time points.
- MDA component (yes/no) response at all time points.

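### Sub-study MDA comparisons make no use of MDA status at the switch visit, so their intervals are wider than the collected data allow

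*SAP*

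**What the plan says.** Protocol Appendix 10 Section 9.3 sets the method: "Binary endpoints (eg, MDA response) will be analyzed using the normal approximation for the difference in binomial proportions", with missing responses counted as non-response. SAP Appendix 6 Section 7.1.2 repeats it: "Two-sided p-value and 95% CI will be generated by normal approximation to the binomial distribution approach for the treatment comparison between the 2 groups". The formula given there is a raw difference with an unpooled standard error. Section 7.2.2 sends MDA response and "MDA component (yes/no) response at all time points" to that formula.

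SAP Appendix 2.8 defines MDA as meeting at least five of seven criteria at the visit. It makes no reference to baseline.

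Other sub-study efficacy endpoints do take baseline into account:
- **Continuous endpoints:** Section 5.4 says of the MMRM that "The baseline value will be included in the model as a covariate".
- **Dactylitis and enthesitis:** Table 3 restricts the analysis to subjects affected at baseline. It has no row for MDA.
- **PsARC:** SAP Appendix 2.4 defines response by percent change from baseline.

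On design, SAP Appendix 6 Section 1 says "Subjects will be randomized to the 2 treatment arms in a 1:1 ratio". Neither that section nor Protocol Appendix 10 Section 5.1 names a stratification factor. Protocol Appendix 10 Section 9.1 says "This is an estimation study" and "A sample size of 90 subjects per group was selected", and it justifies that number by interval half-width.

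**The concern.** Subjects enter the sub-study after at least 24 months of tofacitinib in the extension study, so a fair share may already be in MDA when methotrexate is withdrawn or continued. For a status endpoint, status at the switch is likely to be a strong predictor of status six months later. All seven criteria are scheduled at each extension visit that can serve as the switch visit (Protocol Sections 6.2.2 to 6.2.4), so the predictor can be derived without new data.

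Leaving it out makes the interval for the treatment difference wider than it need be. In a study sized on interval width, that is a cost against the plan's own criterion. MDA status is also not among the baseline characteristics listed in SAP Appendix 6 Section 7.3.1, so a chance difference between arms at the switch might not be displayed.

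**Working it through.** **Inputs.** From the documents: 90 per arm, 1:1 allocation, two-sided 95% intervals, and the Section 7.1.2 formula. Assumed, because the documents give no MDA rates: b, the share in MDA at the switch; p1 and p0, the probability of MDA at the later visit for subjects in and not in MDA at the switch.

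**The plan's own figures.** Half-width = 1.96 × SD × √(2/90).
- HAQ-DI: 1.96 × 0.6 × 0.1491 = 0.175, stated as about 0.18.
- PASDAS: 1.96 × 1.6 × 0.1491 = 0.467, stated as about 0.47.

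Both reproduce.

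**MDA, raw against stratified.** Let p = b·p1 + (1−b)·p0.
- Raw half-width = 1.96 × √[2p(1−p)/90].
- Stratified half-width = 1.96 × √{2[b·p1(1−p1) + (1−b)·p0(1−p0)]/90}.

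With b = 0.45:

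| p1 / p0 | p | Raw (points) | Stratified (points) | Narrower by |
|---|---|---|---|---|
| 0.6 / 0.3 | 0.435 | 14.5 | 13.8 | 4.6% |
| 0.7 / 0.3 | 0.480 | 14.6 | 13.4 | 8.3% |
| 0.8 / 0.2 | 0.470 | 14.6 | 11.7 | 19.9% |
| 0.85 / 0.15 | 0.465 | 14.6 | 10.4 | 28.4% |

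At 0.8/0.2 the stratified interval is as narrow as a raw one with 90 × 0.2491/0.16 = 140 per arm. For b from 0.3 to 0.6, the 0.6/0.3 case gives 4.1 to 4.7%. With no link (0.4/0.4) simulation gives half-widths of 14.2 raw and 14.3 stratified, so almost nothing is lost.

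**Effect of missing as non-response.** Suppose 0.8/0.2 applies before that rule and 15% are missing whatever their switch status (assumption). The rates become 0.68/0.17, p = 0.3995, total variance 0.2399 and within-stratum variance 0.1755. √(0.1755/0.2399) = 0.855, so the gain falls from about 20% to about 14%.

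**Imbalance and width are the same variance.** At 0.8/0.2 the SD of the between-arm difference in switch MDA is √(2 × 0.45 × 0.55/90) = 0.074. Multiplied by the slope p1 − p0 = 0.6, it moves the raw difference by 0.0445 (1 SD). The raw variance minus the stratified variance is 0.005536 − 0.003556 = 0.00198, and √0.00198 = 0.0445. The imbalance term is exactly what the raw interval carries and the stratified one removes.

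**Validity by simulation.** 20,000 trials, b = 0.4, 0.8/0.15, no true effect:
- Bias is about 0 for both estimates.
- Overall coverage is 0.943 raw and 0.948 stratified.
- Among trials with an imbalance of at least 10 points in one direction, coverage is 0.811 raw and 0.942 stratified. An absolute imbalance of that size occurs in about 17% of trials at b = 0.4.

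**Same quantity estimated.** With an effect of −20 points only among subjects in MDA at the switch and b = 0.45, the population difference is 0.45 × (−20) = −9.0 points. In simulation raw and Mantel-Haenszel both average −9.0.

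**Components.** The same formula applies with b as the share meeting that component. If 90% meet it at the switch and 0.8/0.2 holds, p = 0.74 and √(0.16/0.1924) = 0.912, a gain of 8.8%. The other stratum would hold only about 9 subjects per arm.

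**The case against.** The strongest reply is that this is an efficiency preference. An unadjusted risk difference is a valid randomized comparison, the protocol names the method for MDA, and SAP Appendix 6 Section 3 has no hypotheses or decision rules. The low coverage appears only in trials selected for a large imbalance in one direction. All of this stands, and it limits the point to precision.

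Stakes are modest. Precision was planned for the change in HAQ-DI and PASDAS, both adjusted for baseline. The measures behind the MDA components are also analysed by baseline-adjusted MMRM (BSA and LEI only in subjects above zero at baseline). This stands too. It does not make the MDA interval itself narrower, and the protocol attaches nominal significance to two-sided p-values at 0.05 in this sub-study.

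The planned analysis of subjects with at least five swollen or tender joints does not fill the gap. It depends on sample size and is a subgroup, not an adjustment.

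A practical objection also stands: stratification needs more detail than naming the stratum. The skin criterion can be met through PASI or BSA. PASI is scheduled at extension visits, including the switch, but later sub-study visits collect BSA only. SAP Appendix 2.8 allows MDA to be missing, and the Section 7.1.2 adjustment for 0% or 100% response is written per arm. The fix has to settle these.

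**Conclusion.** The point holds as a precision improvement that should be made. MDA response and its components are the sub-study efficacy endpoints with neither a baseline adjustment nor a baseline restriction, and the data to adjust them are already scheduled. Under assumed rates the 95% interval narrows by 4 to 5% with a weak link, about 20% at 0.8/0.2 and about 28% at 0.85/0.15, less if missing-as-non-response dilutes the link. The component gains are less certain, and sparse strata are possible.

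Three stronger readings are not supported:
- A reader might infer that the planned MDA comparison is biased or invalid. Under 1:1 randomization its bias is about 0 and its overall coverage about 0.94.
- A reader might count chance imbalance at the switch as a second harm beside the wider interval. The variance identity shows that they are one.
- A reader might infer that the raw difference answers the wrong question because it mixes subjects who could lose MDA with subjects who never had it. The stated objective is efficacy of monotherapy compared with background methotrexate, and a Mantel-Haenszel difference averages over the same two groups. Only a separate table of MDA kept and lost addresses retention.

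**What to change.** Amend SAP Appendix 6 Section 7.1.2 as follows:

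- For MDA response, and for each MDA component where both strata contain subjects in both arms, report the Mantel-Haenszel risk difference stratified by whether that criterion was met at the Switch/Baseline visit. Use the Sato variance with a normal 95% interval and p-value.
- Keep missing as non-response for post-baseline responses.
- Derive the skin criterion from BSA ≤3% at both the switch and later visits, because PASI is not collected during the sub-study.
- Place subjects with missing switch status in the stratum that did not meet the criterion.
- If a stratum is empty in an arm, use the existing raw formula. This depends on switch data alone, not on outcomes.
- State that the existing 0.5 adjustment belongs to the raw formula, and keep the rule of no formal comparison when both arms are at 0% or both at 100%.
- Keep the raw difference as supportive. Tabulate MDA kept and lost by arm among subjects in MDA at the switch.

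The cost is a few SAP lines and one derived stratification variable per endpoint. The method remains a normal-approximation difference in proportions, as the protocol requires.
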